5.5.1.4. Additional considerations

For clinicaltrials.gov and EudraCT posting purposes, a summary of combined solicited and unsolicited non-serious adverse events will be produced by System Organ Class and preferred terms and according to occurrence of each event.

5.5.2. Concomitant Medication

Medications will be coded using the WHODrug dictionary. The frequencies and percentages of subjects starting concomitant medications after vaccination will be tabulated by vaccine group.

6. ANALYSIS INTERPRETATION

The primary objective is divided in three primary endpoints. The first one regards safety and will be only descriptive. The two other endpoints will be achieved if non-inferiority is demonstrated. Non-inferiority is demonstrated if for each of the four serogroups A, C, W and Y (the four serogroup B test strains: M14459, 96217, NZ98/254 and M07-0241084), the lower limit of the 2-sided 95% confidence interval of the between-group ratio of hSBA GMTs is >0.5 for group MenB+MenACWY versus group MenACWY (for group MenB+MenACWY versus group MenB).

6.1. Hypotheses related to primary immunogenicity objectives

The statistical hypotheses and analyses are based on the common assumption that the logarithmically (base of 10) transformed hSBA titers are normally distributed.

Non-inferiority of concomitant rMenB+OMV NZ with MenACWY to rMenB+OMV NZ

The null (not non-inferiority) and the alternative (non-inferiority) hypotheses are:

$$H_{0,i}^{MenB} : \mu_{A, MenB,i} - \mu_{B, MenB,i} \leq \log_{10}(0.5) \text{ versus}$$

$$H_{1,i}^{MenB} : \mu_{A, MenB,i} - \mu_{B, MenB,i} > \log_{10}(0.5),$$

where $i=1,\dots,4$ is an index over the four serogroup B strains M14459, 96217, NZ98/254 and M07-0241084, and $\mu_{A, MenB,i}$ and $\mu_{B, MenB,i}$ are the population means of the logarithmically (base of 10) transformed hSBA titers for the i^{th} serogroup B strain at one month after the second vaccination in Groups MenB+MenACWY and MenB respectively.

Non-inferiority of concomitant rMenB+OMV NZ with MenACWY to MenACWY

The null (inferiority) and the alternative (non-inferiority) hypotheses are:

$$H_{0,j}^{MenACWY} : \mu_{A, MenACWY,j} - \mu_{C, MenACWY,j} \leq \log_{10}(0.5) \text{ versus}$$

$$H_{1,j}^{MenACWY} : \mu_{A, MenACWY,j} - \mu_{C, MenACWY,j} > \log_{10}(0.5),$$

where $j=1,\dots,4$ is an index over the four serogroups A, C, W and Y, and $\mu_{A, MenACWY,j}$ and $\mu_{C, MenACWY,j}$ are the population means of the logarithmically (base of 10) transformed hSBA titers for the j^{th} MenACWY serogroup at one month after the first vaccination in Groups MenB+MenACWY and MenACWY respectively.

The threshold of $\log_{10}(0.5) = -\log_{10} 2 \approx -0.3$ is the non-inferiority margin.

The 8 hypotheses associated with the primary objective will be tested simultaneously, to control for the type I error rate. The testing of the hypotheses will be done simultaneously on all the strains and serogroups.

6.2. Hypotheses related to secondary immunogeneity objectives

There is a non-inferiority test associated with the concomitant rMenB+OMV NZ with MenACWY to MenACWY using ELISA GMCs.

Non-inferiority of concomitant rMenB+OMV NZ with MenACWY to MenACWY

The null (inferiority) and the alternative (non-inferiority) hypotheses are:

$$H_{0,j}^{MenACWY}: \mu_{A, MenACWY,j} - \mu_{C, MenACWY,j} \leq \log_{10}(0.5) \text{ versus}$$

$$H_{0,j}^{MenACWY}: \mu_{A, MenACWY,j} - \mu_{C, MenACWY,j} > \log_{10}(0.5),$$

where $j=1,\dots,4$ is an index over the four serogroups A, C, W and Y, and $\mu_{A, MenACWY,j}$ and $\mu_{C, MenACWY,j}$ are the population means of the logarithmically (base of 10) transformed hSBA titers for the j^{th} MenACWY serogroups at one month after the first vaccination in Groups MenB+MenACWY and MenACWY respectively.

Non-inferiority of concomitant rMenB+OMV NZ with MenACWY versus MenACWY alone will be claimed if the null hypotheses are rejected for all four serogroups A, C, W and Y, as measured by ELISA GMCs.

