CCI	
 – For a pre-vaccination titer \geq LOD but $<$ LLOQ, a post vaccination titer (Visit 2, Month 1) of at least fourfold the LLOQ, – For a pre-vaccination titer \geq LLOQ, a post vaccination titer (Visit 2, Month 1) of at least fourfold the pre-vaccination titer (for Groups MenB+MenACWY and MenACWY).

*The NHBA indicator strain M07-0241084 may be subject to change during the study, before clinical testing starts. In this case, this change will be documented in the clinical report.

The study will be deemed successful if both:

1. the non-inferiority of the antibody response to rMenB+OMV NZ when given concomitantly with MenACWY versus rMenB+OMV NZ alone and
2. the non-inferiority of the antibody response to MenACWY when given concomitantly with rMenB+OMV NZ versus MenACWY alone are demonstrated.

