10.1.1.2. Secondary Immunogenicity Objectives

There is a non-inferiority test associated with the concomitant rMenB+OMV NZ with MenACWY to MenACWY using ELISA GMCs.

Non-inferiority of concomitant rMenB+OMV NZ with MenACWY to MenACWY

The null (inferiority) and the alternative (non-inferiority) hypotheses are:

$$H_{0,j}^{\text{MenACWY}}: \mu_{A, MenACWY,j} - \mu_{C, MenACWY,j} \leq \log_{10}(0.5) \text{ versus}$$

$$H_{0,j}^{MenACWY} : \mu_{A, MenACWY,j} - \mu_{C, MenACWY,j} > \log_{10}(0.5),$$

where $j=1, \dots, 4$ is an index over the four serogroups A, C, W and Y, and $\mu_{A, MenACWY,j}$ and $\mu_{C, MenACWY,j}$ are the population means of the logarithmically (base of 10) transformed hSBA titers for the j^{th} MenACWY serogroups at one month after the first vaccination in Groups MenB+MenACWY and MenACWY respectively.

Non-inferiority of concomitant rMenB+OMV NZ with MenACWY versus MenACWY alone will be claimed if the null hypotheses are rejected for all four serogroups A, C, W and Y, as measured by ELISA GMCs.

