
To assess the non-inferiority of the responses to MenACWY when given concomitantly with rMenB+OMV NZ to healthy subjects 16-18 years of age compared to MenACWY administered alone as measured by Enzyme-Linked Immunosorbent Assay (ELISA) Geometric Mean Concentration (GMCs) against each of the serogroups A, C, W and Y, at one month after the (study) vaccination with MenACWY.
 
Criterion: Non-inferiority will be demonstrated if for each of the four A, C, W and Y strains, the lower limit of the 2-sided 95% confidence interval of the between-group ratio of ELISA GMCs (MenACWY with rMenB+OMV NZ versus MenACWY alone) is >0.5.
	
Immune response to MenACWY The immune response to MenACWY when administered with/without rMenB+OMV NZ one month after the first vaccination (Visit 2, Month 1, Groups MenB+MenACWY and MenACWY) will be assessed for the serogroups A, C, W and Y as ELISA GMCs.

To assess the immune response to rMenB+OMV NZ in healthy subjects 16-18 years of age against N. meningitidis serogroup B test strains M14459 (fHbp), 96217 (NadA), NZ98/254 (PorA) and M07-0241084 (NHBA), at one month after the first and the second vaccination with rMenB+OMV NZ.
	
Immune response to rMenB+OMV NZ The immune response to rMenB+OMV NZ when administered with/without MenACWY will be evaluated by measuring bactericidal activity against N. meningitidis serogroup B test strains M14459, 96217, NZ98/254 and M07-0241084 in both MenB+MenACWY and MenB Groups as following:
 
 • GMTs at one month after first (Visit 2, Month 1) and second (Visit 4, Month 3) vaccination with rMenB+OMV NZ and Geometric Mean Ratio (GMRs) at one month after the first and the second rMenB+OMV NZ vaccination compared to the baseline at Visit 1, Day 1/Month 0. • The percentage of subjects with hSBA titers \geq Lower Limit of Quantitation (LLOQ) for each and all serogroup B test strains, one month after the first (Visit 2, Month 1) and second (Visit 4, Month 3) vaccination. • The percentage of subjects with fourfold increase in hSBA titers relative to baseline (Visit 1, Day 1/Month 0) defined as: 
 – For a pre-vaccination titer < limit of detection (LOD), a post-vaccination titer (Visit 2, Month 1 and Visit 4, Month 3) of \geq fourfold the LOD or \geq LLOQ, whichever is greater,

CONFIDENTIAL

205419 (MENB REC 2ND GEN-045 (V72_79))

[figure not shown]
Statistical Analysis Plan Amendment 3

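### The secondary IgG non-inferiority claim for MenACWY does not depend on the primary objectives, so type I error is not controlled across the primary and secondary claims

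*SAP*

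**What the plan says.** **Primary objectives.** SAP section 6 requires, for every strain and serogroup, that "the lower limit of the 2-sided 95% confidence interval of the between-group ratio of hSBA GMTs is >0.5". SAP 6.1 adds: "The 8 hypotheses associated with the primary objective will be tested simultaneously, to control for the type I error rate". Protocol section 4 defines success on these two objectives together: "The study will be deemed successful if both" are shown. The IgG objective is not part of that rule.

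**Secondary IgG objective.** SAP section 2 sets the same kind of criterion for each serogroup: "the lower limit of the 2-sided 95% confidence interval of the between-group ratio of ELISA GMCs (MenACWY with rMenB+OMV NZ versus MenACWY alone) is >0.5". SAP 6.2 then gives the decision rule, that non-inferiority "will be claimed if the null hypotheses are rejected for all four serogroups", judged on ELISA GMCs. Protocol 10.1.1.2 has the same rule ("will be claimed if the null hypotheses are rejected for all four serogroups A, C, W and Y").

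**What is absent.** No current section of either document orders the IgG test after the primaries, makes it conditional on them, or gives it a smaller alpha. Protocol Table 23 multiplies the power of all three hypotheses, but that is a power calculation and not a testing rule. The stepwise order shown in the protocol's amendment history is superseded and concerned only the primary hypotheses.

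**The concern.** The plan states an intention to control type I error for the primaries and then adds a third formal claim outside that control. Followed exactly, it would allow non-inferiority of MenACWY to be claimed on IgG after the hSBA co-primary for MenACWY had failed.

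The two claims would be easy to confuse. The secondary hypothesis in SAP 6.2 carries the same heading and the same symbols as the second primary hypothesis in SAP 6.1, and only the final reference to ELISA GMCs tells them apart. Protocol 8.3.3 treats bactericidal activity as the functional measure and accepted surrogate of protection, and ELISA as a measure of the amount of antibody. A fall-back claim would therefore rest on the less functional readout, and SAP section 8 has since moved that readout to a different assay.

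**Working it through.** **Inputs from the documents**
- Each test: lower limit of a two-sided 95% interval above 0.5, so one-sided alpha 0.025 (SAP sections 2 and 6).
- Decision rules: all 8 primary tests for study success; all 4 IgG tests for the IgG claim.
- Planning values: true ratio 0.9, margin 0.5, 250 evaluable per group, upper-limit SDs from protocol Table 19.
- Correlations between test statistics: not given, so assumed and shown as a range.

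**Step 1. Reproduce the stated power.** On the log10 scale the distance from the margin is log10(0.9/0.5) = 0.2553. The noncentrality is 0.2553 / (SD × √(2/250)), with 498 degrees of freedom. For IgG serogroup A this is 0.2553 / (0.77338 × 0.08944) = 3.69, giving 95.76% as in Table 22. Multiplying within each family gives:

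| Hypothesis | Computed | Stated |
|---|---|---|
| 1, MenB hSBA | 96.81% | 96.81% |
| 2, MenACWY hSBA | 98.47% | 98.47% |
| 3, MenACWY IgG | 94.65% | 94.65% |
| All three | 90.23% | 90.23% |

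**Step 2. Error rate of each claim alone.** Because all tests in a family must pass, the false-claim rate is largest when one null sits at the margin and the other ratios are well above it. That maximum is 2.5% for study success and 2.5% for the IgG claim.

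**Step 3. Error rate over both claims, as now written.** With one limiting null at the margin in each family and correlation r between the two limiting statistics:

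P(at least one false claim) = 0.025 + 0.025 − P(Z₁ > 1.96 and Z₂ > 1.96; r)

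| Assumed r | P(at least one false claim) | Relative to 2.5% |
|---|---|---|
| 0 | 1 − 0.975² = 4.94% | 1.98 |
| 0.5 | 4.54% | 1.82 |
| 0.8 | 3.90% | 1.56 |
| 0.9 | 3.52% | 1.41 |

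With no assumption about r, the bound is 2.5% + 2.5% = 5.0%.

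**Step 4. Simulation of all 12 tests.** Settings: 250 per group, 400,000 draws, limiting tests at the margin and all others at ratio 0.9. Assumed correlations were 0.3 within a family, 0.1 between MenB tests and the others, and 0.24 between hSBA and IgG for different serogroups.

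| Limiting pair | Same-serogroup hSBA–IgG r | False study success | False IgG claim | Either |
|---|---|---|---|---|
| MenB strain M14459 and IgG-A | 0.6 | 2.5% | 2.5% | 4.9% |
| hSBA-A and IgG-A | 0.6 | 2.5% | 2.5% | 4.4% |
| hSBA-A and IgG-A | 0.8 | 2.5% | 2.5% | 3.9% |

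**Step 5. With the IgG test conditional on both primaries.** If any primary null is true, an IgG claim can occur only together with a false study success, so the total is at most 2.5%. If no primary null is true, the only possible error is the IgG claim, again at most 2.5%.

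**Step 6. Power after the change.** Both primaries succeed with probability 0.9681 × 0.9847 = 0.9533. The condition therefore blocks the IgG claim 1 − 0.9533 = 4.7% of the time. The probability of an IgG claim becomes 0.9465 × 0.9533 = 90.2%, which is the overall power already in Table 23.

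**The case against.** The strongest reply is that the plan never promised control beyond the primaries. The IgG objective is labelled secondary, it is worded as assessing where the primaries are worded as demonstrating, and its claim is limited to ELISA GMCs. That is fair as a reading of the intended ranking. It does not settle the matter, because SAP 6.2 and protocol 10.1.1.2 both attach an unconditional claim to the result.

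A reader might infer that the false-claim rate simply doubles. The documents do not support that. The 4.9% figure is a ceiling that needs one limiting null at the margin in each family and nearly uncorrelated statistics, as for a MenB strain paired with an IgG serogroup. The fall-back case, where the same MenACWY serogroup is limiting on both assays, uses the same groups and the same Visit 2 samples. Positive correlation is expected there, and the rate is lower.

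The 2.5% baseline also depends on what counts as a claim. SAP section 6 gives each primary objective its own criterion ("The two other endpoints will be achieved if non-inferiority is demonstrated"). If the two are counted as separate claims, adding IgG moves the ceiling from 4.94% to 1 − 0.975³ = 7.31%, a factor of 1.48.

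A reader might also infer that the IgG claim weakens the primary result or could rescue a failed one. It can do neither: study success depends on the primary objectives alone, whatever the IgG result.

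**Conclusion.** The gap is real but minor. Type I error is controlled for the 8 primary hypotheses through the study-success rule, but not across the primary and secondary claims. Against that rule, the chance of at least one false claim can rise from 2.5% to at most 4.9% for uncorrelated or positively correlated tests. It is about 4.5% to 3.5% for assumed correlations of 0.5 to 0.9, and about 4.4% to 3.9% in the same-serogroup case (assumed 0.6 to 0.8). If several ratios within a family sit at the margin together, the rates are lower still. The study-success conclusion stays at or below 2.5% throughout. What is exposed is the additional IgG claim, above all one made for MenACWY after its hSBA co-primary has failed.

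**What to change.** Add to SAP 6.2 that IgG non-inferiority is tested confirmatorily only if both primary immunogenicity objectives are met, and is otherwise reported descriptively with its confidence intervals. Record this in SAP section 8 as a change from protocol 10.1.1.2, since the protocol wording would otherwise remain unconditional.

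The sample size and the 90.23% overall power do not change, because Table 23 already requires all three hypotheses. The cost is that the stand-alone probability of an IgG claim falls from 94.65% to about 90.2% under the protocol's independence assumption. The condition blocks the claim about 4.7% of the time, including when only a MenB strain fails. If the sponsor finds that too strict, the minimum alternative is to keep the test and label its result as not controlled for multiplicity.

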7. CONDUCT OF ANALYSES

7.1. Sequence of analyses

The final study report will contain at least the final analyses of all primary and secondary endpoints. **CCI** [REDACTED]

Description	Disclosure Purpose (CTRS=public posting, SR=study report, internal)
Final Analysis (Analysis_E1_01)	Public disclosure, Study report

7.2. Statistical considerations for interim analyses

NA

8. CHANGES FROM PLANNED ANALYSES

The electrochemiluminescence-based (ECL) multiplex assay will be used instead of an Enzyme-Linked Immunosorbent Assay (ELISA) to assess the Geometric Mean Concentration (GMCs) against each of the serogroups A, C, W and Y.

The objectives reported in Section 2 will not be changed to maintain the alignment with the study Protocol. Nevertheless, all the outputs generated for the final analysis will reference the actual assay methodology implemented to obtain the results.

This change will also be documented in the Clinical study Report (CSR) as stated in Appendix 2 Section 12.2 of the Protocol.

9. NON-STANDARD DATA DERIVATION RULES AND STATISTICAL METHODS

The following sections describe additional derivation rules and statistical methods which are not presented in Section 10.1.

9.1. Data derivation

NA

9.2. Statistical Method

NA

10. ANNEXES

For database studies an annex describing the data extraction including extraction criteria and variables should be added.

10.1. Business rules for standard data derivations and statistical methods

This section contains GSK Vaccines' standard rules for data display and derivation for clinical and epidemiological studies. These rules will be applied along with those detailed in Section 9 (additional study-specific rules).

10.1.1. Attributing events to vaccine doses

The dose relative to an event is the most recent study dose given to a subject prior to the start of a given event. For example, if the start date of an adverse event is between Dose 1 and Dose 2, the relative dose will be Dose 1.

If an event starts on the same day as a study dose, the relative dose will be derived from the additional information provided in the CRF using the contents of the flag indicating if the event occurred before or after vaccination. If 'after vaccination' is selected, the relative dose for the event will be the one administered on the start day of the event. If 'before vaccination' is selected, the relative dose for the event will be the dose prior to this one.

10.1.2. Handling of missing data

10.1.2.1. Dates

When partially completed dates (i.e. with missing day or month) are used in calculations, the following standard rules will be applied:

- A missing day will be replaced by 15
- A missing day and month will be replaced by June 30th.

The following exceptions apply:

- Adverse event start dates with missing day:
 - If the event starts in the same month as at least one of the study doses, the contents of AE.AESTRTPT (the flag indicating if the event occurred before or after vaccination) will be used to complete the date. If "after vaccination" is selected, the imputed start date will match the first (or only) study dose given during that month. If 'before vaccination' is selected, the imputed date will be one day before the first (or only) study dose given during that month.
- Adverse event start dates with missing day and month:
 - If the event starts in the same year as at least one of the study doses, the contents of AE.AESTRTPT (the flag indicating if the event occurred before or after vaccination) will be used to complete the date. If "after vaccination" is selected, the imputed start date will match the first (or only) study dose given during that year. If 'before vaccination' is selected, the imputed date will be one day before the first (or only) study dose given during that year.

All other cases of incomplete AE or concomitant medication/vaccination start date will follow the standard rules above.

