12.5.4. Unsolicited adverse events

An unsolicited adverse event is an adverse event that was not solicited using a Subject Diary and that was spontaneously communicated by a subjects/parent(s)/LAR(s) who has signed the informed consent. Please see Section [12.5.3.1](#) for more detail, where the criteria are listed.

Parent(s)/LAR(s) will be instructed to contact the site as soon as possible to report potential unsolicited AEs that required hospitalization, or emergency room visit, or visit to/by a health care provider that were of concern to the subjects/parent(s)/LAR(s). The detailed information about the reported unsolicited AEs will be collected by the qualified site personnel during the interview and will be documented in the subject's records.

Unsolicited AEs will be collected during interview with the subjects/parent(s)/LAR(s) and by review of available medical records at the next visit. Unsolicited AEs will be reviewed at the safety follow-up calls as well.

All unsolicited AEs will be collected during the first 30 days after the first (Visit 1), second (Visit 3) and third (Visit 4) injection. Unsolicited AEs leading to vaccine/study withdrawal, medically attended AEs, AESI and SAEs will be collected during the entire study period starting from signature of informed consent until study termination.

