2. OBJECTIVES/ENDPOINTS

Objectives and endpoints are detailed in the table below:

Objectives	Endpoints
	Primary

To assess the safety and tolerability of rMenB+OMV NZ and MenACWY, when administered concomitantly or alone, in healthy subjects 16-18 years of age.
	
 • The frequencies and percentages of subjects with solicited local (i.e., injection site pain, erythema, swelling, induration) and systemic (i.e., fever [temperature $\geq 38.0^{\circ}\text{C}/100.4^{\circ}\text{F}$], nausea, fatigue, myalgia, arthralgia, headache) adverse events (AEs) during the 7 days (including the day of vaccination) following the first (Visit 1, Day 1/Month 0), the second (Visit 3, Month 2) and the third (Visit 4, Month 3) vaccination for all groups. • The frequencies and percentages of subjects with any unsolicited AEs (including all SAEs), AEs leading to withdrawal and medically attended AEs during the 30 days (including the day of vaccination) following the first (Visit 1, Day 1/Month 0), the second (Visit 3, Month 2) and the third (Visit 4, Month 3) vaccination for all groups. • The frequencies and percentages of subjects with SAEs, AEs leading to withdrawal, and medically attended AEs, throughout the study period (Day 1/Month 0 to Month 9). • The frequencies and percentages of subjects (who received rMenB+OMV NZ) with AESI throughout the study period (Day 1/Month 0 to Month 9). • Among subjects who are followed for 12 months after their last dose: 
 ○ The frequencies and percentages of subjects with SAEs, AEs leading to withdrawal, between SFU 5/Month 9 and SFU 7/Month 15 ○ The frequencies and percentages of subjects (who received rMenB+OMV NZ) with AESI between SFU 5/Month 9 and SFU 7/Month 15.

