5.5.1.3. Analysis of Unsolicited Adverse Events

All safety analyses will be performed using the Exposed set.

This analysis applies to all AEs occurring during the study, judged either as probably related, possibly related, or not related to vaccination by the investigator, recorded in AE eCRF, with a start date on or after the date of first vaccination. All AEs starting prior to the first vaccination will only be listed. The original verbatim terms used by investigators to identify AEs in the eCRFs will be mapped to preferred terms using the MedDRA dictionary. The AEs will then be grouped by MedDRA preferred terms into frequency tables according to system organ class.

All reported AEs, as well as AEs judged by the investigator as at least possibly related to study vaccine, will be summarized according to system organ class and preferred term within system organ class. These summaries will be presented by vaccination group and by interval of study observation. When an AE occurs more than once for a subject, the maximal severity and strongest relationship to the group will be counted.

Separate summaries will be produced for the following categories:

- Serious adverse events (SAEs)
- Adverse Events of Special Interest (AESIs) for subjects who received rMenB+OMV NZ

- Adverse events that are possibly or probably related to vaccine.
- Adverse event leading to withdrawal with relationship to COVID-19.
- Adverse events leading to a medically attended visit.

The frequencies and percentages of subjects who reported at least one immediate unsolicited adverse event (i.e., reactions that occurred during the first 30 minutes after any vaccination that have been flagged as immediate in the eCRF and have not been reported in the eDiary) following any study vaccination will be reported by study group.

Data listings of all AEs will be provided by subject. In addition, AEs in the categories above will be provided as listed data.

Between groups assessment

No statistical tests for between-group comparisons will be performed.

- The percentages of subjects with any unsolicited AEs (including all SAEs) during the 30 days (including the day of vaccination) following the first (Visit 1), the second (Visit 3) and the third (Visit 4) vaccination for all groups will be calculated.

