10.1.3.11. Duration of events

The duration of an event with a start and end date will be the number of days between the start and end dates plus one day, i.e. an event that starts on 03MAR2018 and ends on 12MAR2018 has a duration of 10 days.

The duration of solicited adverse events is derived assuming that the solicited adverse event occurred continuously from the first day to the last day the event was reported, regardless of how many days the event was documented in between (i.e., $end\ date - start\ date + 1$).

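### An AE start date with a missing day is set to the 15th of a dose-free month even when the AE's recorded end date is earlier, so an event that must have begun inside the 30-day window can be counted outside it

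*SAP*

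**What the plan says.** SAP 10.1.2.1 gives two standard rules for partial dates: "A missing day will be replaced by 15", and "A missing day and month will be replaced by June 30th". The AE exception for a missing day is limited to one situation: "If the event starts in the same month as at least one of the study doses". In that case the before/after-vaccination flag places the event on the dose date or the day before it. A parallel exception covers a missing day and month when the year contains a dose. Everything else falls back on the standard rules: "All other cases of incomplete AE or concomitant medication/vaccination start date will follow the standard rules above". The section names no bound at the AE end date, the date of report or the last contact. SAP 9.1, where a study-specific derivation would sit, is marked not applicable.

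These dates feed an endpoint under the primary safety objective. SAP section 2 counts subjects with unsolicited AEs "during the 30 days (including the day of vaccination) following the first (Visit 1, Day 1/Month 0", and likewise after the second and third vaccinations; SAP 5.5.1.3 repeats this. Protocol 12.5.4 sets the matching collection period: "All unsolicited AEs will be collected during the first 30 days after the first (Visit 1), second (Visit 3) and third (Visit 4) injection". SAP 10.1.3.10 derives onset day from the start date, with the vaccination day as Day 1. For duration, SAP 10.1.3.11 says it "will be the number of days between the start and end dates plus one day".

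**The concern.** A start date imputed later than the AE's recorded end is impossible on the data held. The end date may also prove that the event began within 30 days of the dose. If the rule still dates it past Day 30, the subject can drop out of the 30-day percentage for a reason unrelated to what happened.

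The dosing schedule makes this reachable. Doses are planned for Days 1, 61 and 91. The 30-day window after doses 1 and 3 usually runs into a calendar month with no dose, which is where the exception stops and the 15th takes over. The percentages at stake are descriptive, but some categories are sparse, and one misplaced event shows there.

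**Working it through.** **Inputs.** Imputed day: 15 (SAP 10.1.2.1). Window: Days 1 to 30, so it closes at dose date + 29 days (SAP section 2 and 5.5.1.3). Onset day = start − dose + 1 (SAP 10.1.3.10). Duration = end − start + 1 (SAP 10.1.3.11). Doses at 0, 60 and 90 days (SAP section 3). I take an event to be in the window when its derived start date is, in line with SAP 10.1.1, which attributes events to doses by start date.

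**1. The plan's own figure.** SAP 10.1.3.11 gives 3 to 12 March 2018 as 10 days: 12 − 3 + 1 = 10. Reproduced.

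**2. Worked example (dates assumed).** Dose 1 on 10 March; nominal dose 2 is 60 days later, on 9 May, so April has no dose. The window closes on 8 April. The AE start is recorded as April with no day; its end is 5 April.

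| Date | Onset day |
|---|---|
| 1 April, earliest possible start | 23 |
| 5 April, latest possible start (recorded end) | 27 |
| 8 April, window closes | 30 |
| 15 April, start under the SAP rule | 37 |

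Every possible start is inside the window. The imputed start is 7 days beyond Day 30 and 10 days after the event ended.

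**3. Which dose dates are exposed.** For a dose on day d of a 31-day month, the window closes on day d + 29 − 31 = d − 2 of the next month. It reaches that month when d ≥ 3, and the 15th lies outside it when d − 2 < 15, that is d ≤ 16. So days 3 to 16 are exposed. In a 30-day month the close is day d − 1, giving days 2 to 15. In a 28-day February it is day d + 1, giving days 1 to 13.

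**4. Enumeration over 730 first-dose dates (2021–2022).**
- Doses 1 and 3, nominal spacing: the window reaches a dose-free next month for 694 of 730 dates, and the 15th lies after the window closes for 334. That is 334/694 = 48.1%, or 334/730 = 45.8% of all dates.
- Dose 2, nominal spacing: 0, because dose 3 almost always falls in the next month.
- Shortest and longest allowed spacing (Protocol Table 4): dose 1, 24.9% and 45.8% of dates; dose 2, 19.5% and 41.1%.

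These are shares of dose dates, not of AEs.

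**5. Share of AEs, under assumptions.** Take dose dates and onsets as uniform, mean AE duration as 6 days, and no dose in the next month. About 11.6% of missing-day AEs truly inside the window are then dated outside it. In only about 6% of missing-day in-window AEs does the rule remove an event whose end date alone proves it belongs. If 2% to 5% of AE start dates lack a day (an assumption; the documents give no figure), that is 0.02 × 6% = 0.12% to 0.05 × 6% = 0.30% of in-window AEs.

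**6. The opposite error.** Dose on 20 March: the window closes on 18 April, and 15 April is Day 27. An AE that began on 25 April (Day 37) and is recorded only as April is dated inside the window.

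**7. Effect of a cap at the end date.** In step 2 the start becomes the earlier of 15 April and 5 April, namely 5 April: Day 27, inside the window, duration 5 − 5 + 1 = 1 day.

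**The case against.** The strongest objection is about weight. Safety is descriptive, with no between-group tests; the endpoint counts subjects rather than events; and all arms share the rule, so it gives no obvious advantage to any. It errs both ways (step 6), so the net direction is unclear, particularly for SAEs and medically attended AEs, which are collected throughout. SAEs must be reported within 24 hours and source data are verified, so missing days should be rare. The rule is also a sponsor-wide standard. All of this stands as to size. None of it justifies a start date after a recorded end date.

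Three stronger readings are tempting and are not supported:

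- **Events lost from Day 1 to Month 9.** A reader might infer that a start imputed after the final Day 271 call drops the event from that endpoint. SAP 5.5.1.3 covers all AEs during the study that start on or after first vaccination and sets no upper date. SFU 5 itself may fall 173 to 201 days after Visit 4 (Protocol Table 5). What remains is narrower: in subjects followed to Month 15, an event near SFU 5 may be put in the wrong one of the two reporting periods.
- **Negative durations in the results.** The example does give 5 − 15 + 1 = −9 days. But the planned duration summaries in SAP 5.5.1.1 cover solicited AEs only, which come from a daily eDiary designed to block incomplete entries (Protocol 12.5.8). No duration summary is planned for unsolicited AEs.
- **A dose-free month leading to 30 June.** With the month missing, the year exception applies whenever any dose fell in that year. The 30 June date is reached only in a dose-free year.

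**Conclusion.** The rule is wrong as written, with a small effect. For missing-day AE starts in a dose-free month it can override a recorded end date and move an event that provably began within 30 days out of the primary 30-day unsolicited-AE percentage. At nominal spacing the calendar allows this for about 46% of dose-1 and dose-3 dates. It happens only when the start day is missing and the end date falls on or before the window's close. Without such an end date (or report date), the true onset is not known to be in the window, and the rule contradicts nothing.

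The number of AEs affected cannot be taken from the documents. Under the assumptions in step 5 it is a few per thousand in-window AEs at most. The arithmetic on dates rests only on the SAP; the share of AEs rests on the assumed uniform dates, 6-day mean duration and 2% to 5% missing days. No bias between arms is shown, and no conclusion of the trial is at risk. It is worth correcting because the correction is so cheap.

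**What to change.** Add to SAP 10.1.2.1: an imputed AE start date may not be later than the AE end date, the subject's last contact date or, where the eCRF records it, the date the AE was first reported. If the 15th or 30 June is later than any of these, use the earliest of them, but for an event flagged as after vaccination do not go earlier than the dose it follows. Keep the same-month and same-year exceptions.

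The last-contact bound also covers a dose-free year. For example, with Day 1 on 1 September 2022 and Day 271 on 29 May 2023, an AE recorded only as 2023 would otherwise be dated 30 June 2023.

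The cost is one sentence in the SAP and a few lines of code. The end-date and last-contact bounds need no new data. The first-report bound is conditional because the documents do not show that this date is captured. The cap does not cure the opposite error, where an event that began after the window is dated inside it.
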